## 6.4. Recurrence or occurrence of secondary malignancy and Survival Follow-Up

Follow-up for recurrence or occurrence of a secondary malignancy must be collected at each clinic visit as per protocol. All patients will be followed up (regardless of the duration of treatment) until the time for final analysis, every 16 weeks for the first 3 years from initiation of study treatment (also, at the end of treatment) and every 6 months thereafter for the remainder of follow-up period\*. If new anti tumor therapy is initiated for either recurrence or occurrence of a secondary malignancy at any time during this period, this and all other pertinent data obtained should be recorded on the appropriate CRFs. The final analysis of primary endpoint (DFS) will be performed when approximately 245 DFS events have been reached.

\* Patients who complete 3-year treatment will be followed up for DFS every 6 months from the date of CT or MRI at the end of study treatment.

Patients who withdraw from treatment before DFS events will be followed up for DFS every 16 weeks from the date of CT or MRI at the withdrawal. After 3 years from initiation of study treatment, CT or MRI for DFS will be performed every 6 months from the first scan date that is performed after more than 3 years from initiation of study treatment.

All patients will be followed up for OS status (regardless of the duration of treatment) approximately every 16 weeks from DFS events until the time for final DFS analysis. Survival status can be ascertained by telephone contact.

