## 7.1.1. Primary Endpoint

DFS is defined as the time interval from the date of randomization to the first date of recurrence (distant or local recurrence of RCC) or the occurrence of a secondary malignancy or death. The primary DFS analysis will be based on assessments by the IRC. IRC will review all imaging data. Additionally, in cases for which there is site confirmation of recurrence or occurrence of a secondary malignancy in the absence of IRC imaging

confirmation, available local histo-/cytopathology reports will also be reviewed by the IRC oncologist to determine confirmation of recurrence or occurrence of a secondary malignancy.

Recurrence refers to relapse of the primary tumor in situ or at metastatic sites. The date of recurrence or the occurrence of a secondary malignancy is defined as the date of the tumor scan or the date of collection of the histo-/cytopathological specimen (for patients who have site confirmation of recurrence or occurrence of secondary malignancy in the absence of IRC imaging confirmation) that demonstrated unequivocal recurrence or a secondary malignancy according to protocol criteria. If both imaging and histo-/cytopatholigical confirmation of recurrence or sencondary malignancy are available, the earlier of the two dates will be considered.

For patients with no DFS event, DFS time will be censored at the date of the last scan prior to the time for the analyses. Patients alive who do not have post-baseline disease assessments will have their DFS times censored at randomization. For patients receiving further anti-tumor therapy prior to recurrence or occurrence of a secondary malignancy or death, DFS will be censored on the date of the last scan prior to taking the anti-tumor medication. Patients who miss 2 or more consecutive tumor scans immediately followed by an event will be censored at the date of the last objective tumor assessment prior to the missing/not readable scans.

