## 10. Appendix B

### Data Handling for DFS Events That Occurred after Two or More Consecutively Missed or Not Readable Scans

Section 5.1 of the SAP states the following: “For subjects who had two or more consecutively missed or not readable IRC reviewed scans immediately prior to a recurrence or occurrence of a secondary malignancy or death,

[figure not shown]
- DFS will be censored on the date of the last IRC reviewed scan prior to the consecutively missed or not readable IRC reviewed scans.”

Subjects in this trial are being followed for recurrence or occurrence of a secondary malignancy every 16 weeks during the first 3 years of treatment after randomization and every 6 months after the first 3 years of treatment. Since the frequency of tumor scans varies depending on whether the tumor scan is within 3 years from randomization or after 3 years from randomization, the length of time interval for two consecutively missed tumor scans can be different.

There are 3 scenarios to determine whether a DFS event should be censored due to 2 or more consecutively missed tumor scans. In order to simplify the description of the 3 scenarios, the following abbreviations are defined:

| Definition  | Abbreviation                  |
|---|-------------------------------|
| date of the last evaluable scan prior to the DFS event  | last-non-missing-date         |
| date for the first missed tumor scan that is after the last non-missing tumor scan prior to the DFS event                         | 1 st -missed-date  |
| date for the 2 nd consecutively missed tumor scan that is after the last non-missing tumor scan prior to the DFS event | 2 nd - missed date |
| date of 3 years after randomization date  | 3-Year (YR) rand date         |

(1) The last-non-missing-date is 16 weeks or more before the 3-YR rand date.

In Scenario (1), the targeted date for the 1st-missed-date is 16 weeks after the last-non-missing-date,

|           |   |                 |           |
|-----------|---|-----------------|-----------|
| Document: | C:\Users\q764206\AppData\Local\Microsoft\Windows\Temporary Internet Files\Content.Outlook\GWW33WM3\ATLAS_SAPFinal v8.0_06MAR2018.docx | Version Number: | Final 8.0 |
| Author:   | [name] (Updated [name]; [name]; [name], [name])  | Version Date:   | 06MAR2018 |

Template No: CS\_TP\_BS016 – Revision 2  
 Effective Date: 01Feb2010

[figure not shown]
Reference: CS\_WI\_BS005

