Statistical Analysis Plan

---

and the targeted date for the 2nd-missed-date is 32 weeks after the last non-missing-date. After adding a 2-week window, the decision rule is: if the DFS event is >34 weeks after the last non-missing date, DFS time will be censored at the date of the last non-missing tumor scan prior to the DFS event, otherwise DFS time will be the non-censored time interval from randomization date to the date of DFS event.

- (2) The last-non-missing-date is before the 3-YR rand date, but the last-non-missing-date plus 16 weeks is beyond the 3-YR rand date.

In Scenario (2), the targeted date for the 1st-missed-date is 16 weeks after the last-non-missing-date, and the targeted date for the 2nd-missed-date is 16 weeks plus 26 weeks after the last-non-missing-date. After adding a 2-week window, the decision rule is: if the DFS event is >44 weeks) after the last-non-missing-date, DFS time will be censored at the date of the last non-missing tumor scan prior to the DFS event, otherwise DFS time will be the non-censored time interval from the randomization date to the date of DFS event.

- (3) The last-non-missing-date is beyond the 3-YR rand date.

---

Document: C:\Users\q764206\AppData\Local\Microsoft\Windows\Temporary Internet Files\Content.Outlook\GWW33WM3\ATLAS\_SAPFinal v8.0\_06MAR2018.docx  
 Author: [name] (Updated [name]; [name]; [name], [name])      Version Number: Final 8.0

Version Date: 06MAR2018

Template No: CS\_TP\_BS016 – Revision 2  
 Effective Date: 01Feb2010

Reference: CS\_WI\_BS005

Statistical Analysis Plan

---

Partial dates should be presented as --NOV1999 or - - - - - 1999 as needed.

Partial times should be presented as --:30 or 14:-- as needed.

Listings should be sorted according to the order of the columns.

---

|           |   |                 |           |
|-----------|---|-----------------|-----------|
| Document: | C:\Users\q764206\AppData\Local\Microsoft\Windows\Temporary Internet Files\Content.Outlook\GWW33WM3\ATLAS_SAPFinal v8.0_06MAR2018.docx |                 |           |
| Author:   | [name] (Updated [name]; [name]; [name], [name])  | Version Number: | Final 8.0 |
|           |   | Version Date:   | 06MAR2018 |

Template No: CS\_TP\_BS016 – Revision 2  
Effective Date: 01Feb2010

Reference: CS\_WI\_BS005

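### SAP Appendix B, Scenario (2): the 44-week limit can censor a 3-year completer's DFS event after one missed scan when the end-of-treatment scan is the last evaluable scan and precedes the third anniversary of randomization

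*SAP*

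**What the plan says.** The rule itself is in Protocol 7.1.1: "Patients who miss 2 or more consecutive tumor scans immediately followed by an event will be censored". SAP 5.1 repeats it, and Appendix B cites SAP 5.1 before giving the operational version.

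Appendix B sorts subjects by where the last evaluable scan lies relative to the "date of 3 years after randomization date". Scenario (2) is: "The last-non-missing-date is before the 3-YR rand date, but the last-non-missing-date plus 16 weeks is beyond the 3-YR rand date". It puts the first missed scan at 16 weeks, and the second "is 16 weeks plus 26 weeks after the last-non-missing-date". It then allows some slack ("After adding a 2-week window") and concludes: "if the DFS event is >44 weeks) after the last-non-missing-date, DFS time will be censored at the date of the last non-missing tumor scan". Treatment completers are not distinguished from subjects who withdrew early.

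Protocol 6.4 gives these two groups different schedules. For completers, with the clock restarted at the end-of-treatment scan: "Patients who complete 3-year treatment will be followed up for DFS every 6 months from the date of CT or MRI at the end". By contrast, subjects who withdrew from treatment before a DFS event stay on 16-weekly scans and go 6-monthly from their first scan after 3 years.

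**The concern.** Scenario (2) uses the withdrawers' spacing for everyone. A completer whose last evaluable scan is the end-of-treatment scan has no scan due at 16 weeks; the next two are due at 26 and 52 weeks. Suppose that scan falls just before the third anniversary of randomization, the 26-week scan is missed, and recurrence is found on time at 52 weeks. One scan was missed, but 52 exceeds 44, so the recurrence is censored back to the end-of-treatment scan.

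A death at week 48 after that scan shows the conflict within the SAP. The footnote to Appendix A Table 1 counts a death before two scheduled assessments have been missed as an event, provided no anti-tumor therapy came first. On the Protocol 6.4 schedule that death qualifies, yet Scenario (2) censors it. Two programmers could code it differently.

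Valid events would be dropped from the primary analysis in a group defined after randomization, whose size may differ between arms. Tables 3 (investigator DFS) and 5 (new therapy as event) take their missed-scan definition from the same appendix.

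**Working it through.** **Limits.** Appendix B's method is: weeks to the first missed scan + weeks from there to the second + 2.

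- Scenario (1), as stated: 16 + 16 + 2 = 34. Reproduced.
- Scenario (2), as stated: 16 + 26 + 2 = 44. Reproduced.
- Completer whose last evaluable scan is the end-of-treatment scan (Protocol 6.4): 26 + 26 + 2 = 54.

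For this completer Scenario (2) is 54 − 44 = 10 weeks short.

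| Event, weeks after end-of-treatment scan | 6-monthly scans missed (due at 26 and 52, +2 weeks) | Censored at 44? | Censored at 54? |
|---|---|---|---|
| 40 | 1 | no | no |
| 45 | 1 | yes | no |
| 52 | 1 | yes | no |
| 54 | 1 | yes | no |
| 55 | 2 | yes | yes |

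Only events more than 44 and up to 54 weeks after the scan are misclassified.

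**Can a completer be in Scenario (2)?** The last 16-weekly scan before 3 years is at week 144. Three years is 1095/7 = 156.4 weeks, so that scan is 12.4 weeks earlier and outside the 8-week allowance in Protocol 6.2.3. A separate end-of-treatment scan is normally needed. Treatment starts 0–7 days after randomization (Protocol 4.3). I counted the share with start delay + treatment duration + scan offset below 1096 days, giving every day equal weight (an assumption):

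| Treatment duration | Scan 0 to +7 days from last dose | Scan −7 to +7 days | Scan up to 8 weeks before |
|---|---|---|---|
| 1096 days | 0% | 23% | 92% |
| 1092 days (39 cycles of 28 days) | 16% | 50% | 98% |
| 1082 days (SAP 7.4.3 counts >1081 as 36 months or more) | 98% | 99% | 100% |

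The share therefore depends on treatment duration and scan timing, which the documents do not fix.

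**Size.** Inputs from the plan (SAP 3.3):

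- Retention at 36 months, if 23% drop-out by 18 months continues at a constant rate: 0.77² = 0.59.
- 3-year DFS under the exponential assumption is the 2-year rate to the power 1.5. Placebo: 0.9×0.70^1.5 + 0.01×0.35^1.5 + 0.09×0.33^1.5 = 0.55. Axitinib: 0.9×0.79^1.5 + 0.01×0.61^1.5 + 0.09×0.51^1.5 = 0.67. Mean 0.61.
- Event-free and in follow-up at 3 years: 0.59 × 0.61 = 0.36, before any allowance for stopping treatment because of toxicity.
- Followed a further year: about half, since with even accrual over 24 of 60 months half have at least 48 months.

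Assumed, with no source in the documents: 0–50% of completers in Scenario (2), 5–15% miss the 26-week scan, and 6–16% of those have an event in the affected interval.

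- Upper: 700 × 0.36 × 0.5 × 0.5 × 0.15 × 0.16 = 1.5 events.
- Lower: 0, if no end-of-treatment scan precedes the anniversary.
- If every completer were in Scenario (2), the upper figure would double to 3.0.

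**The case against.** The strongest defence is that this is a corner case. Four conditions must hold together: the end-of-treatment scan is the last evaluable one, it precedes the anniversary, the 26-week scan is missed, and the event falls in a 10-week band. Treatment starts on or after randomization, so a subject treated for a full 3 years and scanned at or after the last dose lands on or beyond the anniversary. No passage defines 3 years as 39 cycles, and the ±7-day imaging window is stated for the 16-weekly scans. The rule is the same in both arms, and the planned analysis without missed-scan censoring (SAP 7.3.1, Appendix A Table 4) keeps every such event. All of this stands, and it limits the size of the point.

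It does not remove the error. The SAP supersedes the protocol, but its introduction reserves major changes to the primary analysis for a protocol amendment, and Appendix B presents itself as applying the two-scan rule, not changing it. Table 4 is a sensitivity analysis and does not correct the primary one.

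Three stronger readings are tempting and not supported:

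- That completers in general lose events after one missed scan. Outside the conditions above they do not.
- That 44 weeks is wrong for everyone in Scenario (2). It matches the schedule of early withdrawers.
- That a scan a few days later would save the event under Scenario (3). The text available gives only the entry condition, "The last-non-missing-date is beyond the 3-YR rand date". Its limit is not visible, so nothing can be said about it.

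**Conclusion.** The point holds in narrow form. For a 3-year completer whose end-of-treatment scan is the last evaluable scan and precedes the third anniversary of randomization, Scenario (2) censors events more than 44 and up to 54 weeks later although only one scan has been missed. That departs from Protocol 7.1.1, SAP 5.1 and the Table 1 footnote, and it carries into Tables 3 and 5. The mismatch follows from the text alone.

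The number of events does not. Roughly 0 to 1.5 of 245 is an illustration that rests on the assumed Scenario (2) share, missed-scan rate and event rate. A reader might infer that the primary result is materially biased or that the arms are affected unequally; the documents give no basis for either. Severity is minor. It is worth correcting because a primary-endpoint rule should apply its own definition.

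**What to change.** Before unblinding, amend Appendix B so that missed scans are counted from each subject's own scheduled dates under Protocol 6.4, plus the 2-week window.

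Equivalently, add to Scenario (2): if the last evaluable scan is the one that restarts the 6-monthly schedule for a subject recorded as completing 3-year treatment, the target dates are 26 and 52 weeks after it, and DFS is censored only if the event is more than 54 weeks after it. Keep 44 weeks for all others.

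Either way, the appendix should say which record defines completion, which scan serves as the restart when an earlier scan within 8 weeks replaces the end-of-treatment scan or that scan is missing or unreadable, and whether the 3-year date runs from randomization (Appendix B) or treatment start (Protocol 6.4). Tables 1, 3 and 5 then follow through their reference to Appendix B.

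The cost is a sentence or two of SAP text and one programming condition. It needs no new data, no change to the scan schedule and no change to the 245-event target.
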